13.8 Methods for additional analyses (e.g. subgroup analyses)

Subgroup analyses will include looking at the stratifying factors of Tanner stage (2/3 vs 4/5), birth registered sex (male/female), and whether there is a neurodevelopmental trait or disorder diagnosis (yes/no). Also assessed will be the length of GnRHa treatment received over the duration of the trial.

The statistical analysis plans for the respective studies will further define subgroups to be analysed, and the analysis to be carried out on these subgroups.

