Summary of Eligibility Criteria:	
Inclusion Criteria
 
 1. Participating in the PATHWAYS HORIZON study 2. Has agreed to be contacted for other research studies 
Exclusion Criteria
 
 1. Is considered clinically eligible for GnRHa and wishes to receive this intervention 2. A decision regarding clinical eligibility for GnRHa is pending 3. CYP has previously used GnRHa or gender-affirming hormones for gender incongruence

Study Synopsis

Title Of Clinical Trial:	Puberty Suppression And Transitional Healthcare with Adaptive Youth Services (PATHWAYS): PATHWAYS CONNECT
Protocol Short Title/ Acronym:	PATHWAYS CONNECT
Study Phase:	Observational
Sponsor Name(s):	King's College London South London and Maudsley NHS Foundation Trust
Chief Investigator(s):	[name] [name] (Deputy CI)
Medical Condition or Disease Under Investigation:	Gender Incongruence
Purpose of Clinical Trial:	To determine whether GnRHa during puberty in CYP with gender incongruence affects brain development.
Primary Objective:	To map trajectories of brain development in CYP with gender incongruence, comparing those receiving GnRHa immediately (two years) vs delayed start (one year) with a non-randomised comparison group from HORIZON INTENSIVE not receiving GnRHa
Secondary Objective(s):	To link trajectories of brain development to cognitive measures, including general intelligence, memory and executive function.
Trial Design:	Longitudinal observational study comparing participants from TRIAL and HORIZON INTENSIVE.
Sample Size:	250 participants (150 from TRIAL, 100 from HORIZON INTENSIVE).
Summary of Eligibility Criteria:	
Inclusion Criteria
 
 Participant is a member of PATHWAYS TRIAL or PATHWAYS HORIZON INTENSIVE. Participant is willing to participate in brain imaging study, including travelling to London (King's College London). Participant provides informed assent (for u16) or consent (for 16+). Parent/legal guardian provides consent. 
Exclusion Criteria
 
 MR imaging is contra-indicated (e.g. ferromagnetic metal implants).

The electronic version of this document is the latest version. It is responsibility of the individual to ensure that any paper material is the current version. Printed material is uncontrolled documentation.

Revision History

Protocol version	Description of changes from previous revision	Effective Date

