1.5.4 Long-term benefits

Gender incongruence can be a long-standing, even life-long, experience. Hence, it is important to ensure long-term follow-up of any interventions in childhood and adolescence, to understand their impact in adult life. It has been suggested that a short-term clinical trial lasting for 2 years will not help to address the question of whether GnRHa is beneficial. This is incorrect for several reasons. First, one of the reasons for offering GnRHa is to manage immediate (short-term, during treatment)

The electronic version of this document is the latest version. It is responsibility of the individual to ensure that any paper material is the current version. Printed material is uncontrolled documentation.

levels of emotional distress regarding pubertal changes and allow young people time to explore their identity. However, the currently available evidence (described above) is inconsistent in whether GnRHa has positive short-term benefits. An RCT of limited duration can answer these questions. Second, long-term effects can only be evaluated following research examining short- or medium-term effects. There are many examples of this in relation to lifelong conditions. For example, it was important to document the short-term benefits of stimulant medication in ADHD before examining longer-term effects.

In summary, an RCT of GnRHa in children and young people with gender incongruence is ethically sound because of clinical equipoise and the need to conduct the study in this age group. The study is rigorous in eliciting clinical eligibility and informed assent/consent., processes to safeguard the best interests of children and young people, described below. Alternative study designs are not able to provide the needed quality of evidence to determine the benefits and harms of this intervention.

2 Trial Design

The PATHWAYS TRIAL is designed as a Randomised Controlled Trial (RCT) comparing immediate vs. delayed start (at 1 year post-randomisation) of GnRHa amongst 226 CYP with primary endpoint at 2 years post-randomisation. Midpoint comparisons determine short-term differences due to receipt of GnRHa while endpoint comparisons determine whether the groups converge or GnRHa timing/duration influences outcome. All participating CYP and their parents/legal guardians will be asked to assent/consent to longer-term follow-up, which in the first instance will be for the life of the funding (total period 5.5 Years).

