2.4.3 Exploratory Objectives

1. Do short-term/risk benefit profiles vary according to chronological age and/or Tanner stage?
2. Do risk benefit profiles vary according to birth-registered sex?
3. Do risk benefit profiles vary according to presence or not of neurodevelopmental disorders or high levels of neurodevelopmental traits?
4. Do risk benefit profiles vary according to length of GnRHa treatment?

3 Participants

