5.2 Intervention and comparator description, dosing and labelling and intervention

5.2.1 Medication:

The primary intervention all participants will initiate treatment on is Decapeptyl® SR (long-acting formulation of Triptorelin) 22.5mg intramuscular injection (6 monthly preparation).

5.2.2 Labelling:

The information presented on the IMP labels will be annex 13 compliant.

5.2.3 Administration:

The dose of Decapeptyl SR (long-acting formulation of Triptorelin) 22.5mg is administered every six months at 0, 6, 12, 18, and 24 months post-randomisation. This dosing regimen is in adherence to the approved schedule in the Decapeptyl SmPC for the indication of precocious puberty in the same age group, used in routine clinical care. In cases of documented tolerability issues, inadequate suppression of puberty, or product unavailability, alternative regimens may be implemented in accordance with expert panel recommendation and confirmation, as outlined in Appendix C with the following products:

- Decapeptyl® SR (long-acting formulation of Triptorelin) 11.25mg intramuscular injection (3 monthly preparation)
- Prostap 3 DCS (Leuprorelin Acetate) 11.25mg intramuscular injection (3 monthly preparation)
- Gonapeptyl (Triptorelin) 3.75mg intramuscular injection (1 monthly preparation)

5.2.4 Monitoring:

Following administration, participants will be monitored during their clinic visit for any immediate adverse reactions post-injection. The length of the monitoring period is determined by the principal or sub-investigator at the endocrine centre based on their clinical expertise.

Regular follow-up appointments to assess efficacy and safety, including monitoring hormone levels and physical development.

Routine blood tests, DEXA scans, and physical assessments (height, weight, BMI, blood pressure, body composition using Tanita scales if available, and puberty staging).

Psychosocial screening to identify any unmet needs and escalate these to appropriate services.

5.2.5 Fertility Preservation:

Discussion of fertility preservation options with referrals to fertility specialists if desired.

5.2.6 Comparator:

Delayed Start: Participants in the delayed start group will begin GnRHa treatment one year after randomisation. They will receive the same monitoring and assessments as the immediate start group.

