5.6 Discontinuing allocated interventions

Participants may discontinue GnRHa treatment at any time without any detrimental impact on their care. Reasons for discontinuation will be documented, and participants will remain in follow-up according to their randomised arm's schedule of events until the end of the study .

Health care team-initiated discontinuation criteria include:

- Occurrence of any condition that, in the opinion of the Investigator, significantly jeopardizes the wellbeing and safety of the patient, including serious or intolerable AE that prevents the subject from continuing with study participation

The electronic version of this document is the latest version. It is responsibility of the individual to ensure that any paper material is the current version. Printed material is uncontrolled documentation.

- Change in compliance with any inclusion or exclusion criterion that is clinically relevant and affects subject safety, as determined by the Investigator.
- Use of prohibited concomitant medications
- QTc > 470ms
- Pregnancy

When the health care team are considering discontinuation, they will discuss the reasons for this with the participant and their parents/ legal guardians, taking account of their preferences and possible alternative treatment regimes.

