13.5 Statistical methods for primary and secondary outcomes

13.5.1 Statistical methods for primary outcome

13.5.1.1 Trial

The primary estimand is a treatment policy estimand. This means that intercurrent events are not taken into account when the analysis is performed. This is similar to how an intention to treat analysis would be carried out. The specification of the estimand is below.

The electronic version of this document is the latest version. It is responsibility of the individual to ensure that any paper material is the current version. Printed material is uncontrolled documentation.

- **Population** – CYP with gender dysphoria who are in the CYPGS and are determined to be clinically eligible for GnRHa treatment and meet the eligibility criteria for the trial.
- **Endpoint** – The endpoint is 24-months post randomisation into the trial.
- **Treatment condition** – Treatment is GnRHa, either immediately or delayed for a year. The delayed treatment is the control treatment, and the treatment arm is the immediate arm.
- **Intercurrent event** – Intercurrent events are as below:
 - Failure to adhere to randomised treatment protocol – Non-compliance with the prescribed treatment regimen, including missed doses or incorrect administration
 - Premature discontinuation of the randomised treatment – Participants stopping the treatment before the study endpoint for any reason.
 - Death of participant during the trial period
 - Long-term physical or mental health hospital admission – Hospital admissions for physical health reasons that extend beyond a short-term stay and could impact the study outcomes
 - Serious adverse events that significantly impact the participant's health and require medical intervention (such as a severe allergic reaction)
 - Substance abuse: Development of substance abuse issues during the trial period
 - Pregnancy
 - Major changes in lifestyle or environment that could impact the participant's health or adherence to the trial protocol, such as relocation
- **Population level summary** – The population level summary will be the difference between the two arms at 24-months, as measured by the mean of the posterior, with the 95% credible interval.

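### Section 13.8 lists length of GnRHa treatment received, a post-randomisation variable, beside the baseline subgroup factors and does not tie exploratory objective 4 to the randomised month-24 contrast

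*Protocol*

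**What the plan says.** Exploratory objective 4 (synopsis and section 2.4.3) asks: "Do risk benefit profiles vary according to length of GnRHa treatment". Section 13.8 is where the protocol turns the exploratory objectives into analyses. It names Tanner stage, birth-registered sex and neurodevelopmental status, which match objectives 1 to 3, and then adds "Also assessed will be the length of GnRHa treatment received over the duration of the trial", which matches objective 4. Detail is deferred: "The statistical analysis plans for the respective studies will further define subgroups to be analysed".

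Elsewhere the protocol treats duration through the randomised arms. Section 2 says that "endpoint comparisons determine whether the groups converge or GnRHa timing/duration influences outcome", and section 2.2 says that the endpoint results inform on timing and cumulative effects. Section 13.10.1 analyses everyone in the arm to which they were randomised. Section 13.8 does not refer to any of this when it reaches treatment length.

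On stopping, section 5.6 says: "Participants may discontinue GnRHa treatment at any time without any detrimental impact on their care". It also lists reasons for which the care team may discontinue treatment, among them serious or intolerable adverse events, a QTc criterion, prohibited medication and pregnancy. Those who stop remain in follow-up (sections 4.8, 4.14.10 and 5.6).

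**The concern.** The three stratifiers are fixed before allocation, so arms can be compared fairly within their levels. Length received is known only afterwards. It is set first by arm and then by whatever made someone stop, not start or miss injections. No cut-point chosen later in the SAP can turn it into a baseline factor, so the problem lies in the variable that the protocol names and not in missing detail.

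If participants who are doing badly stop sooner, short exposure will be associated with poor outcome even when duration does nothing. For adverse events the link is more direct, because an event can itself end treatment. A result suggesting that longer treatment is better, or safer, could then come from who stopped. Duration is a central benefit–risk question in this trial, and such a finding would be read closely.

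**Working it through.** **1. Planned exposure by month 24.** Inputs: the immediate arm starts at month 0. For the other arm, section 5.2 says "Participants in the delayed start group will begin GnRHa treatment one year after randomisation". Section 13.5.1.1 says "The endpoint is 24-months post randomisation into the trial". Exposure = endpoint − start:

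- Immediate: 24 − 0 = 24 months.
- Delayed: 24 − 12 = 12 months.

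This reproduces the two years and one year given in the CONNECT synopsis.

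**2. Visit windows** (section 4.2.1: month 12 ± 4 weeks, month 24 ± 8 weeks).

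- Delayed, longest: 52 + 4 + 8 = 64 weeks, about 14.8 months.
- Delayed, shortest: 52 − 4 − 8 = 40 weeks, about 9.2 months.
- Immediate, full course: 24 months ± 8 weeks, about 22.2 to 25.8 months.

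Participants who follow the schedule fall into two separate ranges, one per arm. Lengths between or below those ranges arise mainly from stopping, not starting or missed doses.

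**3. Who falls where.** Take 113 per arm (Table 1), 6-month steps, and an assumed share s of the immediate arm stopping by month 24. With a constant risk at each later injection, h = 1 − (1 − s)^(1/3). The immediate-arm counts are 113h, 113(1−h)h, 113(1−h)²h and 113(1−s); the delayed-arm counts are 113h and 113(1−h).

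| s (assumed) | Immediate at 6 / 12 / 18 / 24 months | Delayed at 6 / 12 months |
|---|---|---|
| 5% | 1.9 / 1.9 / 1.9 / 107.3 | 1.9 / 111.1 |
| 10% | 3.9 / 3.8 / 3.6 / 101.7 | 3.9 / 109.1 |
| 20% | 8.1 / 7.5 / 7.0 / 90.4 | 8.1 / 104.9 |
| 30% | 12.7 / 11.2 / 10.0 / 79.1 | 12.7 / 100.3 |

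On this nominal grid the 18- and 24-month groups are all immediate arm. The 12-month group is nearly all delayed-arm completers plus a few immediate-arm stoppers.

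**4. Size of a spurious effect.** Null simulation: 113 per arm, SD 10 (section 13.4.1), no effect of arm or duration, and 1,000 runs per cell. Stopping follows a latent variable with assumed correlation r to the month-24 score, with lower scores stopping sooner. The protocol gives neither s, r nor the direction.

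| s | r | Slope on length, points per 12 months (rejection at nominal 5%) | Same, adjusted for arm | Randomised contrast | Correlation of length with arm |
|---|---|---|---|---|---|
| 10% | 0 | 0.04 (5%) | 0.08 (5%) | 0.02 | 0.89 |
| 10% | 0.3 | 1.31 (18%) | 6.14 (59%) | 0.02 | 0.89 |
| 10% | 0.5 | 2.14 (40%) | 9.95 (95%) | 0.03 | 0.88 |
| 20% | 0 | −0.02 (6%) | 0.01 (5%) | −0.03 | 0.79 |
| 20% | 0.3 | 2.06 (39%) | 5.35 (74%) | 0.03 | 0.79 |
| 20% | 0.5 | 3.41 (77%) | 8.97 (100%) | 0.01 | 0.79 |
| 30% | 0 | 0.00 (6%) | 0.00 (4%) | 0.00 | 0.69 |
| 30% | 0.3 | 2.67 (60%) | 5.11 (85%) | 0.06 | 0.70 |
| 30% | 0.5 | 4.36 (95%) | 8.48 (100%) | −0.03 | 0.69 |

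Adjusting for arm makes the bias larger, because only the stopping-driven variation in length is then left. The randomised contrast stays at about zero throughout. The simulation omits the baseline score and repeated measures of the primary model; adjusting for baseline would remove whatever part of the association it explains.

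**The case against.** The strongest reply is that 13.8 covers additional analyses, says only that length is also assessed, fixes no cut-point or contrast, and leaves the method to the SAP. The analysis is exploratory and the main duration question is handled elsewhere. Much of this stands, and it limits the point in four places where a reader might infer more:

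- **That objective 4 is answered only by received length, so that randomisation is discarded.** Sections 2, 2.2 and 13.10.1 keep the randomised endpoint comparison and give timing and duration to it. What is missing is the link from 13.8.
- **That there can be no delayed-arm participants above 12 months.** This is true only of nominal visit times; the windows allow about 64 weeks.
- **That the analysis compares dropouts with completers.** Those who stop treatment stay in follow-up, so they are treatment discontinuers with outcomes.
- **That the bias is certain and as large as the 5.25-point design effect.** It depends on assumed stopping and correlation and vanishes if stopping is unrelated to outcome. Some reasons listed in section 5.6, such as pregnancy or prohibited medication, need not track quality of life.

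A further objection concerns the remedy. Using arm as an instrument for months received would need arm to act only through months received. Section 2.2 expects direct allocation effects, through expectancy and through possible deterioration in delayed participants who wanted immediate treatment, and arm also shifts when treatment starts. So the randomised contrast does not isolate duration alone either. This stands and is reflected in the fix.

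The appeal to the SAP does not remove the core point: the protocol has already chosen length received as the variable.

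**Conclusion.** The point holds as a defect in an exploratory analysis that should be corrected. Length received is a post-randomisation variable placed beside baseline factors. It is largely determined by arm (correlation 0.69 to 0.89 under the assumed stopping rates) and otherwise mainly by stopping, some of which section 5.6 ties to adverse events.

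Under 10–30% stopping and a correlation of 0.3–0.5, the spurious effect is 1.3 to 4.4 T-score points per 12 months without adjustment for arm, and 5.1 to 9.9 with it. All of these rest on assumed inputs, including the direction of the association. Only a KIDSCREEN-type score was simulated, so no size is claimed for harm outcomes. The primary analysis is not affected.

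**What to change.** In section 13.8, remove length of treatment received from the subgroup factors. State that exploratory objective 4 is addressed, for each benefit and risk domain, by the randomised immediate-versus-delayed contrast at month 24, read as the combined effect of timing and duration. Report any analysis by received length as descriptive, non-randomised and non-causal, with reasons for stopping shown alongside.

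If a per-month estimate with arm as instrument is added, state that its exclusion restriction is doubtful given the expectancy and timing effects in section 2.2.

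The cost is a wording change in the protocol, carried into the SAP, with no new data. The downside is that the trial will offer no causal estimate for months of treatment actually received.

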13.9 Methods to handle missing data

Where there are two or more post randomisation outcome timepoints, missing assessments will be dealt with by fitting mixed models to all the available data using maximum likelihood methods. Such an approach provides valid inferences under the assumption that the missing data mechanism is ignorable (or Missing At Random, MAR). This approach applies to both TRIAL and HORIZON INTENSIVE.

13.10 Populations under investigation

13.10.1 TRIAL

For TRIAL and CONNECT, all participants randomised will be analysed in the arms which they were randomised to regardless of the intervention they received, under the treatment policy estimand.

13.10.2 HORIZON INTENSIVE

HORIZON INTENSIVE participants will all be analysed in the same arm, as there is no intervention they can receive.

13.11 Methods to handle compliance

Compliance will be defined in the SAP. Non-compliance will be dealt with using sensitivity analyses. These analyses are detailed in section 13.12.

13.12 Sensitivity analysis

A Complier Average Causal Effect (CACE) analysis on the primary outcome will be performed if adherence is found to be low (less than 80% in the study overall). This will only be for Trial analysis.

Additional analyses will be carried out using alternative priors, to assess the robustness of the estimates obtained in the primary analysis. These priors will be used in place of the uninformative priors being used in the primary analysis.

13.13 Plans to give access to the full protocol and participant-level data

It is anticipated the full protocol and all results will be available as open access according to the rules of the funding bodies.

14 Oversight and monitoring

14.1 Programme Management Group (PMG)

The PMG will be chaired by the PATHWAYS CI, [name], with membership comprising co-investigators and core members of the central research team.

14.2 Programme Steering Committee (PSC)

The PSC will be composed of 7 independent members and additional non-independent members; the independence level will be above 75%. Attendance of non-voting members at PSC meetings will be at the discretion of the chair. The PSC is an executive committee, reporting to the funder, the National Research Collaboration Programme (NRCP), and the trial sponsors.

The PSC is formally appointed by the National Institute for Health and Care Research (NIHR) and members will receive individual letters from the NIHR confirming their role. Independent members will be independent of the Sponsor organisations and of any recruiting study sites.

The PSC will agree the frequency of meetings prior to the start of the trial; however, it is likely the PSC will meet at least bi-annually.

The trial may be prematurely discontinued by the Sponsor, Chief Investigator or Regulatory Authority on the basis of new safety information or for other reasons given by the Data Monitoring Committee / Programme Steering Committee regulatory authority or ethics committee concerned.

If the trial is prematurely discontinued, active participants will be informed, and no further participant data will be collected. The Competent Authority and REC will be informed within 15 days of the early termination of the trial.

The electronic version of this document is the latest version. It is responsibility of the individual to ensure that any paper material is the current version. Printed material is uncontrolled documentation.

